### **9.3 Follow-up of Adverse Events and Serious Adverse Events**

Follow all AEs (serious and non-serious) until resolution or otherwise explained (see Table 16), the subject dies, the event stabilizes and is not expected to further resolve with the maximum time limit for stabilization defined as 30 days after the occurrence of the event, or when alternative therapy is instituted, whichever occurs first. If alternative therapy is instituted, it should be documented (see Section 8.2.4). Enanta Pharmaceuticals, Inc. may request that the Investigator perform or arrange for supplemental measurements or evaluations to further clarify the nature of the event.

### **9.4 Sponsor's Review of Adverse Events and Serious Adverse Events**

Enanta Pharmaceuticals, Inc. will maintain an ongoing review of all AEs and SAEs.

### **9.5 Data Safety Monitoring Board**

Safety data from this study will be reviewed by a Data Safety Monitoring Board (DSMB) throughout the study. The DSMB will be headed by a DSMB Chair and will include physicians with expertise in diseases of the liver including PBC. Procedures for data review including timing and potential outcomes will be governed by the DSMB charter.

## 10. SUBJECT SAFETY MANAGEMENT

In the event that two or more subjects experience a similar drug-related Grade 3 or 4 AE or SAE or Grade 3 or 4 laboratory abnormality, a DSMB meeting will be immediately convened by the Sponsor. Based on the data presented, a decision will be made as to whether or not enrollment should be halted, the study should be halted, or if dosing and enrollment into the study should continue.

### 10.1 Individual Subject Stopping Rules

Study drug will be discontinued in subjects with elevated ALT or AST (see below) and thorough evaluation and follow-up will be performed:

- If ALT or AST increases to  $>5 \times$  Baseline.
- If ALT or AST increase  $>2 \times$  Baseline AND the increase is accompanied by a concomitant TB increase to  $>2 \times$  Baseline OR the INR concomitantly increases by  $>0.2$
- If elevations of ALT/AST are accompanied by signs or symptoms of right upper quadrant abdominal pain, anorexia, nausea, vomiting, fever, eosinophilia, and/or rash.

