### **8.3 Clinical Laboratory and Diagnostic Procedures**

All laboratory samples will be analyzed by a centralized laboratory. A laboratory reference manual will be provided to the site detailing kit contents, reordering supplies, sample collection (see below), handling, storage and shipment instructions. All unblinded laboratory values will be reviewed by the Investigator, documented, and the results maintained in the source documents. All out-of-range lab findings require an interpretation as to whether or not they are clinically significant. Clinically significant laboratory findings in the opinion of the Investigator should be recorded as an AE (or SAE as appropriate).

At all visits blood samples should be collected before the first dose of the study drug. Additional clinical laboratory evaluations will be performed at other times if judged clinically appropriate by the Investigator, or if the safety review of the data suggests a more detailed assessment of clinical laboratory safety evaluations. Any changes to the scheduled times of the clinical laboratory determination will be agreed to by Enanta and the Investigator, and documented in the study trial master file (TMF).

For Biomarker analysis, fasting serum or plasma samples should be collected before the daily dose of study drug for analysis of FGF19, bile acids, C4, and at visits indicated in the SoA (Appendix 1). Samples should be collected after an overnight fast of a minimum of 8 hours.

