**Table 14: Laboratory Evaluations**

CHEMISTRY PANEL Alanine Aminotransferase (ALT/SGPT) Albumin, Serum Albumin/Globulin (A/G) Ratio (calculation) Alkaline Phosphatase, Serum Amylase Aspartate Aminotransferase (AST/SGOT) Bilirubin, Total and Direct BUN BUN/Creatinine Ratio (calculation) Calcium, (Serum) Creatine Kinase Creatinine, Serum (creatinine clearance) Uric Acid Electrolyte Panel (Na+, K+, Cl, Bicarb.) Phosphorus Gamma Glutamyl Transferase (GGT) Globulin, Total Glucose, Serum Cholesterol, serum Lactate Dehydrogenase (LDH) Lipase Protein, Total, Serum TG (triglycerides)
	
HEMATOLOGY PANEL Hemoglobin Hematocrit Differential WBC Count (percentage and absolute): Basophils, Eosinophils, Lymphocytes, Monocytes, Neutrophils MCH MCHC MCV Platelets Red Blood Count RBC Morphology White Blood Count

Coagulation tests INR – PT/PTT
	
SCREENING TESTS Viral serology: HIV-1, HIV-2, HBV (HBsAg), anti-HCV antibodies and HCV RNA PBC diagnostic (if needed): AMA/M2/PBC-ANAb
 
MARKERS OF CV RISKS AND LIPIDS hs-CRP HDL and LDL-P (high and low-density lipoprotein particles using a lipoprotein subfractions test; eg, LIPOPROFILE) lipoprotein (a) [Lp(a)] assay apoA-I, apoB, apoB/A Ratio, apoC3, apoE isoforms (E2, E3, E4) Total Cholesterol (TC) High Density Lipoprotein – Cholesterol (HDL-C) Low-Density-Lipoprotein – Cholesterol (LDL-C) TG (triglycerides) Total/HDL Cholesterol (CT) Ratio Adiponectin

URINALYSIS Routine urinalysis to include: Color and appearance, pH, SG, Bilirubin, Glucose, Ketones, Leukocytes, Nitrite, Occult blood, Protein, Urobilinogen, Microscopic (including RBCs and WBCs)
	
MARKERS OF FIBROSIS AND INFLAMMATION ENHANCED LIVER FIBROSIS (ELF) PANEL - Hyaluronic acid (HA), - Procollagen III amino terminal peptide (PIIINP) - Tissue inhibitor of metalloproteinase 1 (TIMP-1)

PREGNANCY AND MENOPAUSE TESTS Serum pregnancy test Follicle-Stimulating Hormone (FSH)
	
PRO-C3 Fibrinogen, CRP, alpha2 macroglobulin and haptoglobin Tumor necrosis factor alpha and beta (TNF-<math>\alpha</math>, <math>\beta</math>)

BIOMARKERS FGF19 (fasting plasma) Total bile acids (fasting serum) C4 (7<math>\alpha</math>-OH-4-cholesten-3-one)
	
IL-6, IL1<math>\beta</math> AST to Platelet Ratio Index (APRI) Fibrosis 4 (FIB-4) Index

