### 10.2 Management of Liver Enzyme Elevations

The FDA Guidance for Industry for Drug Induced Liver Injury (FDA, 2009) will provide guidance for the management of changes in liver transaminases (ALT/AST) and TB.

The protocol also includes an algorithm to respond to changes in liver enzymes and functions as follow:

- To establish a baseline utilizing at least 2 lab values at least several weeks apart.
- For subjects with elevated baseline liver chemistry that develop AST or ALT elevations  $2 \times$  baseline, subjects will be reassessed promptly (eg, 48-72 hours) with full liver biochemistry and physical exam and if the repeat assessment shows persistent elevations in transaminases, subjects should be followed according to the “close observation” guidelines:
  - Repeat liver enzyme and serum bilirubin tests two or three times weekly. Frequency of repeat testing can decrease to once a week or less if abnormalities stabilize or the trial drug has been discontinued and the subject is asymptomatic.
  - Collect additional PK samples at the same visits as safety labs
  - Obtain a more detailed history of symptoms and prior or concurrent diseases.

- Obtain a history of concomitant drug use (including nonprescription medications and herbal and dietary supplement preparations), alcohol use, recreational drug use, and special diets.
  - Rule out acute viral hepatitis types A, B, C, D, and E; autoimmune or alcoholic hepatitis; NASH; hypoxic/ischemic hepatopathy; and biliary tract disease.
  - Obtain a history of exposure to environmental chemical agents.
  - Obtain additional tests to evaluate liver function, as appropriate (eg, INR, direct bilirubin).
  - Consider gastroenterology or hepatology consultations.
  - Consider liver biopsy for any patient with persistent evidence of liver injury.
- If a subject lives in a remote area, they can be tested locally with the results promptly communicated to the Investigator site.

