 Full PE at Screening and EOS; all other exams should be targeted to review of new signs and symptoms

 Vital Signs include HR, respiratory rate, and BP and will be measured once in the morning before the morning dose of study drug

 Safety laboratory tests include chemistry (including liver function tests), hematology, and urinalysis and should be collected predose at all visits; See Table 14 for details

-  Biomarkers include fasting plasma FGF19, fasting serum bile acids, fasting C4 (7 $\alpha$ -OH-4-cholesten-3-one). Samples should be collected after a minimum 8 hr fast and before the subject takes the daily dose of study drug
-  Lipids and CV risk markers to be collected are detailed in Table 14
-  Markers of inflammation include fibrinogen, CRP, IL6, IL1 $\beta$ , TNF- $\alpha$ , TNF- $\beta$ , alpha2 macroglobulin and haptoglobin (see Table 14)
-  Collect PK/PD samples after a minimum 8 hr fast and before the daily dose of study drug. PK/PD samples on Days 1 and 84 (Week 12) collected predose and 2, 6, and 8 hr postdose; Weeks 2, 4 and 8 at predose and two samples postdose; the first sample collected 1 to 3 hours postdose and the second sample at least 1 hour later.
-  PK predose samples should be collected after a minimum 8 hr fast before the daily dose of study drug. PK samples collected Day 1, Weeks 2, 4, 8 and 12 at predose and two samples postdose; the first sample collected 1 to 3 hours postdose and the second sample at least 1 hour later.
-  Study drug given in the clinic on days where subject is seen in the clinic
-  Additional samples may be collected to further assess safety events e.g. pruritus
- [REDACTED]

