10.2 Laboratory Data

Laboratory test results for Baseline, Week 12 visits, change from Baseline at Week 12 and change to abnormal status of either below LLN ("Low") or above ULN ("High") from Baseline at Week 12 for all Safety Lab tests (Appendix 6) will be summarized by treatment groups. Shift tables will be used to present change in status (normal to abnormal or abnormal to normal) from Baseline at Week 12. All lab values will be listed and all test values outside the normal range will be flagged. Urinalysis results will be summarized separately for continuous and categorical variables. Pregnancy test results will be listed only.

The pre-dose laboratory test results only within the time window will be considered for analyses safety laboratory data summaries.

For average baseline, it is considered the average of the latest (closest to the target day Day -1) laboratory test result in the screening window (from Day -28 to Day -1) and the pre-dose Day 1 laboratory test result.

For Day 1 value or the latest value prior to the first dose of study drug as baseline, it is considered the laboratory test result in the screening window (from Day -28 to Day -1) not beyond Day -28 laboratory test result.

For screening visit as baseline, it is considered the laboratory test result in the screening window (from Day -28 to Day -1) and the latest laboratory test result.

If the recorded the laboratory test result ($<XX.xx$) is below the lower limit, then the value 0.0 is considered for the laboratory test result.

If the recorded laboratory test result ($>XX.xx$) is above the upper limit, then the value of the ($XX.xx$) is considered for the laboratory test result.

For the purposes of summarization in both the tables and listings, all laboratory values will be converted to standardized units. Reference Covance Lab Manual for schedule of testing.

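### Stopping rule 2 depends partly on an INR rise, but neither the protocol nor the SAP requires an on-treatment INR, even after ALT or AST has passed 2× Baseline

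*Protocol*

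**What the plan says.** Protocol 10.1 gives three mandatory stops for an individual subject:

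1. ALT or AST above 5× Baseline.
2. ALT or AST above 2× Baseline with total bilirubin above 2× Baseline "OR the INR concomitantly increases by" more than 0.2.
3. Any ALT/AST elevation accompanied by listed signs or symptoms.

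The Schedule of Assessments (Protocol Appendix 1, repeated in SAP Appendix 5) has a PT/PTT and INR row marked at Screening and End of Study (EOS) only. Footnote 13 defines what is drawn at every visit: "Safety laboratory tests include chemistry (including liver function tests), hematology, and urinalysis and should be collected predose at all visits". Coagulation is not in that list. Protocol Table 14 keeps it as a separate panel, "Coagulation tests".

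When ALT or AST reaches 2× Baseline, Protocol 10.2 asks that subjects be "reassessed promptly (eg, 48-72 hours) with full liver biochemistry and physical exam". If the elevation persists, close observation begins, with repeat liver enzymes and bilirubin. INR appears further down that list: "Obtain additional tests to evaluate liver function, as appropriate (eg, INR, direct bilirubin". Protocol 8.3 adds a general provision: "Additional clinical laboratory evaluations will be performed at other times if judged clinically appropriate by the Investigator", or if safety review of the data calls for more.

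SAP 10.2.1 says subjects are monitored for the INR criterion throughout the study and that its incidence is summarised by treatment group. SAP 10.2 says results and changes "from Baseline at Week 12 for all Safety Lab tests (Appendix 6) will be summarized by treatment groups"; Appendix 6 includes INR, PT and PTT. The same section closes with "Reference Covance Lab Manual for schedule of testing".

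**The concern.** A mandatory stop needs the measurement that triggers it. Here the measurement is left to the investigator's discretion, and at the earliest it is suggested only after a repeat test has shown persistence. By then it may no longer be concomitant with the ALT/AST value that raised the question, and no interval is defined.

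The exposed subjects have ALT or AST above 2× and up to 5× Baseline, bilirubin not above 2× Baseline, and none of the rule 3 signs. For them the INR criterion is the only mandatory individual stop. Protocol 1.2.1 itself describes prothrombin time as an assay of hepatic synthesis.

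There is also a reporting consequence. If INR is not measured, the SAP 10.2.1 tabulation will show the criterion as not met, so rule 2 incidence can be too low without anyone noticing.

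**Working it through.** The plan states no figure to reproduce. The check is a count from the schedule, followed by a comparison of dates.

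**Scheduled draws (Protocol Appendix 1, SAP Appendix 5)**

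| Visit | ALT, AST, bilirubin | INR |
|---|---|---|
| Screening | yes | yes |
| Day 1 (predose) | yes | no |
| Day 3 | yes | no |
| Week 2 | yes | no |
| Week 4 | yes | no |
| Week 8 | yes | no |
| Week 12 / EOT | yes | no |
| EOS | yes | yes |

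The column reading can be verified. The height, weight and BMI row shows the same pattern, and Protocol 8.2.3 says weight is recorded at Screening and EOS.

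- INR is scheduled at 2 of 8 visits, and at 0 of the 5 post-dose visits on treatment.
- Dosing ends on Day 84, so a stop has practical effect at Day 3 and Weeks 2, 4 and 8. INR is scheduled at 0 of these 4.
- Protocol 10.2 makes 0 INR draws mandatory when ALT or AST passes 2× Baseline.
- EOS is four weeks after the last dose (Protocol 7.1.5), so its INR cannot be concomitant with an on-treatment rise.

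**INR level that meets the criterion.** Exclusion 1 (Protocol 3.2) removes INR above 1.2. At that ceiling, 1.2 + 0.2 = 1.4, so the criterion is met at an INR above 1.4 at the latest, and earlier for a lower baseline.

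**Could the EOS draw serve as the Week 12 value?** SAP 6.3 closes the Week 12 window at End of Treatment + 7 days. The EOT visit is Day 84 ± 2.

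- EOT on Day 82: 82 + 7 = Day 89
- EOT on Day 84: 84 + 7 = Day 91
- EOT on Day 86: 86 + 7 = Day 93
- Earliest EOS for a completer: 112 − 2 = Day 110
- Gap: 110 − 93 = 17 days to 110 − 89 = 21 days

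The EOS draw therefore falls in the follow-up window, and no scheduled INR falls in the Week 12 window.

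**How many subjects would need a triggered INR?** The documents give no rate for ALT or AST above 2× Baseline, so this is an assumed range applied to the 119 planned subjects:

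- 1%: 119 × 0.01 = 1.2, about 1
- 5%: 119 × 0.05 = 6.0, about 6
- 10%: 119 × 0.10 = 11.9, about 12

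At 1%, the chance that at least one subject crosses is 1 − 0.99^119 = 0.70. The exposed subjects described above are a subset of those who cross, and the documents do not allow that subset to be sized.

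**The case against.** The strongest reply is that the trigger may exist elsewhere. SAP 10.2 refers the schedule of testing to the central laboratory's manual, and SAP Appendix 6 lists an elevated-liver coagulation panel (INR, PT) under safety monitoring. Its name suggests a panel triggered by liver elevation. Protocol 10.2 also points to external guidance on drug-induced liver injury. This limits the finding, because neither source is available here. But Appendix 6 states no trigger or timing, and a mandatory stop should be workable from the protocol itself. A reflex panel would also not supply routine Week 12 values.

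Second, since rule 2 is mandatory, applying it arguably presupposes an INR. That reading is reasonable, but Protocol 10.2 says what to do at 2× Baseline and leaves INR out of the required tests. Protocol 8.3 permits an INR without naming one.

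Third, other protections remain. Albumin, another marker of synthesis, is in the chemistry panel at every visit. Entry criteria exclude cirrhosis. The investigator may stop drug (Protocol 7.2). Two similar drug-related Grade 3 or 4 events or laboratory abnormalities convene the DSMB (Protocol 10), which also meets after each group of 20 subjects completes four weeks (SAP 12). All of this stands and lowers the risk, but none of it yields an INR value, and albumin does not trigger rule 2.

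Fourth, the assumed crossing counts do not measure harm. Harm would also require an INR rise above 0.2 in a subject caught by no other rule, and an investigator who orders no INR. That is correct; the counts size the extra testing, not the injury.

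**Conclusion.** The concern holds. As written, the INR part of rule 2 has no required on-treatment measurement: 0 of 5 scheduled visits and 0 triggered draws. Rule 2 incidence under SAP 10.2.1 can be under-counted, and the Week 12 coagulation summaries in SAP 10.2 have no scheduled data. The Week 12 mismatch is a reporting matter without a safety consequence of its own.

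This should be fixed, but it does not disable the stopping rules. The bilirubin criterion, the 5× rule and the symptom rule all work on the existing schedule. The conclusion rests on the protocol and SAP alone; a trigger in the laboratory manual would close the safety gap in practice, though not the Week 12 mismatch.

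**What to change.** 1. In Protocol 10.2, require PT/INR at the 48-72 hour reassessment for any subject whose ALT or AST exceeds 2× Baseline, and take INR off the discretionary list. In 10.1, state the interval that counts as concomitant, for example 72 hours to match the reassessment; the sponsor may choose another.
2. Tie the elevated-liver coagulation panel in SAP Appendix 6 to that trigger. If the laboratory manual already contains one, cite it in Protocol 10.2 and Appendix 6.
3. For the Week 12 summaries, either add PT/INR to the Week 12/EOT draw or state in SAP 10.2 that coagulation is summarised at Screening and EOS only.

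PT/INR at other on-treatment visits is optional. The 10.1 thresholds stay as they are.

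The cost is small. Items 1 and 2 need one coagulation tube for each subject who crosses 2× Baseline, about 1 to 12 subjects under the assumed 1% to 10%. Item 3 is at most 119 tubes at an existing visit, or one line in the SAP. No scheduled visit is added. Changing required testing in 10.2 does mean a protocol amendment with ethics review (Protocol 12.1.2 and 12.1.4), and some out-of-range INRs will need interpretation. If the manual already holds the trigger, a citation may be enough for item 2.

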### 10.2 Management of Liver Enzyme Elevations

The FDA Guidance for Industry for Drug Induced Liver Injury (FDA, 2009) will provide guidance for the management of changes in liver transaminases (ALT/AST) and TB.

The protocol also includes an algorithm to respond to changes in liver enzymes and functions as follow:

- To establish a baseline utilizing at least 2 lab values at least several weeks apart.
- For subjects with elevated baseline liver chemistry that develop AST or ALT elevations  $2 \times$  baseline, subjects will be reassessed promptly (eg, 48-72 hours) with full liver biochemistry and physical exam and if the repeat assessment shows persistent elevations in transaminases, subjects should be followed according to the “close observation” guidelines:
  - Repeat liver enzyme and serum bilirubin tests two or three times weekly. Frequency of repeat testing can decrease to once a week or less if abnormalities stabilize or the trial drug has been discontinued and the subject is asymptomatic.
  - Collect additional PK samples at the same visits as safety labs
  - Obtain a more detailed history of symptoms and prior or concurrent diseases.

- Obtain a history of concomitant drug use (including nonprescription medications and herbal and dietary supplement preparations), alcohol use, recreational drug use, and special diets.
  - Rule out acute viral hepatitis types A, B, C, D, and E; autoimmune or alcoholic hepatitis; NASH; hypoxic/ischemic hepatopathy; and biliary tract disease.
  - Obtain a history of exposure to environmental chemical agents.
  - Obtain additional tests to evaluate liver function, as appropriate (eg, INR, direct bilirubin).
  - Consider gastroenterology or hepatology consultations.
  - Consider liver biopsy for any patient with persistent evidence of liver injury.
- If a subject lives in a remote area, they can be tested locally with the results promptly communicated to the Investigator site.

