#### **7.1.3 Baseline Visit (Day1)**

Subjects who meet all inclusion criteria and none of the exclusion criteria will report to the clinic on the morning of Study Day 1 after fasting overnight for a minimum of 8 hours. After a review

of applicable inclusion/exclusion criteria, subjects who continue to satisfy eligibility requirements will be randomized in a 3:3:1 ratio to their treatment group. Predose assessments and procedures will be conducted as noted in the SoA (Appendix 1) and considered Baseline values.

After predose/Baseline study procedures are completed, subjects will receive the first dose of study drug in the clinic on Day 1 followed by PK and biomarker blood draws. Additional PK, C4, FGF19 and Bile Acid samples will be collected from subjects at a subset of sites (PK/PD Substudy) that have the technical capability to collect and process intensive (longer duration) sampling. PK and PD samples will be collected as described in Section 8.4.

Before leaving the clinic, subjects will receive study medication and instructions on how to take the medication at home.

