6.2 Baseline

For the primary endpoint, baseline will be defined in 3 ways: 1.) the average between the screening and the day 1 visits. If either is missing, the non-missing value will be considered baseline for this approach. This is the primary definition for the study 2.) The Day 1 value or the last value prior to first dose of study drug. 3.) The value from the screening visit as the baseline. The primary endpoint will be evaluated using all 3 baseline calculations. For all secondary and safety endpoints, baseline will be defined using method 2.) above.

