10.2.1 Subject Safety Monitoring

Subjects will be monitored throughout the study for the following:

- ALT or AST increase to $>5 \times$ Baseline
- ALT or AST increase $>2 \times$ Baseline AND the increase is accompanied by a concomitant Total Bilirubin increase to $>2 \times$ Baseline OR the INR (prothrombin time / partial thromboplastin time) concomitantly increases from Baseline by >0.2
- Elevated Baseline liver chemistry (AST or ALT elevations $2 \times$ Baseline) will require subjects to be reassessed promptly (within 48–72 hours) with full liver biochemistry and physical exam

- Elevations of ALT/AST accompanied by preferred terms indicating: signs or symptoms of right upper quadrant abdominal pain, anorexia, nausea, vomiting fever, eosinophilia, and/or rash

Incidence of these safety categories will be summarized by treatment group and identified on the listings with laboratory data parameters

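### The liver-safety baseline is stated inconsistently: a single Day 1 value in protocol 7.1.3 and SAP 6.2, two or more values in protocol 10.2, and a mislabelled screening value in SAP 10.2

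*Protocol*

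**What the plan says.** **Protocol 7.1.3 (Baseline Visit).** The Day 1 predose assessments are the baseline: "Predose assessments and procedures will be conducted as noted in the SoA (Appendix 1) and considered Baseline values".

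**Protocol 10.1 (Individual Subject Stopping Rules).** The first rule opens "If ALT or AST increases to" and sets more than five times Baseline. The second is more than twice Baseline together with a bilirubin or INR rise. Baseline is not defined there.

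**Protocol 10.2 (Management of Liver Enzyme Elevations).** The liver algorithm opens with its own instruction: "To establish a baseline utilizing at least 2 lab values at least several weeks apart". It gives no rule for combining the values. The same list then uses twice baseline as the trigger for prompt reassessment.

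**SAP 6.2 (Baseline).** Method 2 is "The Day 1 value or the last value prior to first dose of study drug", and "For all secondary and safety endpoints, baseline will be defined using method 2.) above". The other two methods in that section are for the primary ALP endpoint only.

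**SAP 10.2 (Laboratory Data).** Three laboratory baselines are described. The one labelled as the Day 1 or latest predose value is then defined as follows: "it is considered the laboratory test result in the screening window (from Day -28 to Day -1) not beyond Day -28 laboratory test result".

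**SAP 10.2.1 (Subject Safety Monitoring).** The protocol's 2x and 5x multiples are repeated against Baseline, and "Incidence of these safety categories will be summarized by treatment group and identified on the listings with laboratory data parameters". The section does not say which baseline applies.

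**The concern.** A rule of the form ALT > k x Baseline is only as definite as its denominator. A site that follows protocol 7.1.3 divides by one Day 1 value. A site that follows protocol 10.2 divides by something built from two or more values. A programmer who follows the wording of SAP 10.2 divides by a screening value. The same subject could then be managed as over a limit and tabulated as under it, or the reverse. At stake are the 2x reassessment trigger, possibly the 10.1 multiples, and whether the SAP 10.2.1 incidence table describes what was done at the sites. The primary ALP endpoint has its own stated baseline in SAP 6.2 and is not at issue.

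**Working it through.** The plan gives no figure for this point, so there is nothing to reproduce. The check sets the texts side by side and then shows what the difference does to a multiple.

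**1. The texts compared**

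- *One value or several.* Protocol 7.1.3 and SAP 6.2 method 2 agree whenever a Day 1 value exists. Protocol 10.2 differs from both, and neither document cross-refers to resolve it.
- *Gap between values.* Screening may fall anywhere from Day -28 to Day -1, and the schedule has safety laboratory tests at Screening and Day 1. The two scheduled pretreatment values are therefore 1 to 28 days apart, so a gap of several weeks is possible but not guaranteed.
- *SAP 10.2 against SAP 6.2.* The visit-window table in SAP 6.3 gives Day 1 its own row, so a window of Day -28 to Day -1 excludes it. In SAP 10.2 the preceding sentence, which begins "For average baseline, it is considered the average of the latest (closest to the target day Day -1) laboratory test result", goes on to name the Day 1 predose result as its second component. The next sentence, on the Day 1 baseline, does not. Read literally, it gives the same value as the screening baseline defined after it.
- *INR.* The schedule collects INR only at Screening and end of study, so protocol 7.1.3 supplies no scheduled Day 1 value for the INR limb of 10.1.

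**2. Effect on one subject (ALT values are assumptions)**

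Let s be the screening value and d the Day 1 value. The two-value baseline is taken as the mean (s + d)/2. Averaging is also an assumption, because protocol 10.2 gives no combining rule.

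| s | d | On-treatment ALT | ALT/d | ALT/mean | ALT/s |
|---|---|---|---|---|---|
| 60 | 40 | 220 | 220/40 = 5.50 | 220/50 = 4.40 | 220/60 = 3.67 |
| 40 | 60 | 220 | 220/60 = 3.67 | 220/50 = 4.40 | 220/40 = 5.50 |
| 60 | 40 | 90 | 90/40 = 2.25 | 90/50 = 1.80 | 90/60 = 1.50 |

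In row 1 only the Day 1 baseline puts the subject above 5x. In row 2 only the screening baseline does. In row 3 only the Day 1 baseline exceeds 2x.

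**3. Width of the disagreement band**

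With r = s/d > 1, Day 1 and the mean disagree for ALT between k x d and k x d x (1 + r)/2. Day 1 and Screening disagree between k x d and k x d x r. In multiples of d:

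| r (assumed) | 5x: Day 1 v mean | 5x: Day 1 v Screening | 2x: Day 1 v mean | 2x: Day 1 v Screening |
|---|---|---|---|---|
| 1.1 | 5.00-5.25 | 5.00-5.50 | 2.00-2.10 | 2.00-2.20 |
| 1.5 | 5.00-6.25 | 5.00-7.50 | 2.00-2.50 | 2.00-3.00 |
| 2.0 | 5.00-7.50 | 5.00-10.00 | 2.00-3.00 | 2.00-4.00 |

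**4. Spread under random variation**

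If log ALT varies within a subject with SD σ, the log ratio of one value to the mean of two is about half the difference of the two log values, with SD σ/√2. A 2x rise on the single value then equals 2 x exp(±1.96σ/√2) on the mean (95% range): 1.7-2.3 for σ = 0.1, 1.5-2.6 for σ = 0.2 and 1.3-3.0 for σ = 0.3. The σ values are assumptions.

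**5. Borderline case**

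Suppose the true on-treatment level sits exactly at the multiple and variation is independent and log-normal (assumed CV 10-40%). In simulation, Day 1 and the mean then classify differently in about 17% of cases, and Day 1 and Screening in about 33%, at every CV tried. This describes a subject at the threshold, not the rate expected in the trial.

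**The case against.** Several points on the other side stand and limit the finding.

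- **A reader might count three rival definitions of equal weight.** The texts do not support that. Protocol 7.1.3 and SAP 6.2 agree when Day 1 is present. The screening version rests on one badly worded SAP 10.2 sentence whose opening names Day 1, and which may have been meant only to limit how old a fallback value may be. Since the screening baseline is defined separately in the next sentence, it looks like a drafting slip. Even so, the sentence does not say it is a fallback.
- **A reader might infer that the stopping rules themselves run on two baselines.** That link is inferred. Protocol 10.1 uses the capitalised term that 7.1.3 ties to Day 1, while the two-value instruction sits in 10.2, in lower case, ahead of a monitoring algorithm. On that reading 10.1 and SAP 10.2.1 share the Day 1 value. However, nothing confines the 10.2 instruction to 10.2, and SAP 10.2.1 lists the 10.2 reassessment trigger beside the 10.1 multiples under one undefined Baseline. Also, 2x alone never stops drug under 10.1; a bilirubin or INR rise is required as well.
- **A reader might infer that SAP 10.2 shifts the baseline of every secondary and safety endpoint to Screening.** It does not. The sentence concerns laboratory results only, so vital signs, ECG and questionnaires are outside it. The schedule has no Screening collection of itch scales, PBC-40, FGF19, C4, bile acids, APRI or FIB-4.
- **Screening plus Day 1 may often satisfy 10.2.** Where Fibroscan is needed, protocol 8.3.6 places it after eligibility on screening laboratory values, so a Day -1 screening draw is unlikely for those subjects. Protocol 10.2 also does not require both values to come from within the study. The gap is still not guaranteed.

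**Conclusion.** The point holds as a one-value versus several-value inconsistency in the liver-safety baseline, plus a separate contradiction between SAP 10.2 and SAP 6.2 on the laboratory baseline. It is a contradiction in the text rather than missing detail. Even if the SAP 10.2 sentence is read as a fallback, protocol 10.2 still differs from protocol 7.1.3 and SAP 6.2, and the above-or-below consequence remains.

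The size can only be illustrated: a ratio of 5.5, 4.4 or 3.7 for the same ALT in the worked example, and a 5x band reaching 6.25 (mean) or 7.50 (Screening) times the Day 1 value when the screening value is 1.5 times Day 1. These figures rest on assumed ALT values and variation and, for the two-value baseline, on an assumed averaging rule. The discordance rate in this trial cannot be derived from the documents. The supportable statement is that the SAP 10.2.1 table may not match decisions taken at sites, not that it will fail to. The point should be corrected, but it does not touch the primary analysis.

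**What to change.** 1. **SAP 10.2.** Reword the second baseline sentence to agree with SAP 6.2 for the analysis of laboratory data: the Day 1 predose result, with the last screening-window result only when Day 1 is missing.
2. **Protocol 7.1.3, 10.1, 10.2 and SAP 10.2.1.** These must be reconciled so that each multiple names its baseline, and the SAP table uses the same baseline as the rule it tabulates. If a baseline built from several values is kept anywhere, state how the values are combined and what happens when the required gap is not met. The INR limb should be covered too, since no Day 1 INR is scheduled. Which baseline governs clinical decisions is for the sponsor.

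The cost is wording in the two documents and a matching definition in the program for the SAP 10.2.1 flags. Naming the baselines does not change the sample size or the primary analysis.
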